7.4.6.3. Oral Health Impact profile for TMD (OHIP-TMDs)

This is a validated 22-item self-report instrument examining disorder specific quality of life in TMD. The instrument's minimum additive score is 0 and its maximum is 88 with higher scores equating to worse disorder specific quality of life. Its minimum clinically important difference has been determined as 6.0 (Yule et al., 2015).

7.4.6.4. EQ-5D-5L

This is a validated 5-item self-report instrument examining generic quality of life from which health utilities can be derived. The minimum health utility is -0.59 (a state worse than death), rising to 0 (death) and a maximum utility of 1.0 (state of perfect health).

7.4.6.5. Brief Pittsburgh Sleep Quality Index (BPSQI)

This is a validated 6-item self-report measure examining five features of sleep: quality, latency, duration, efficiency, and disturbance. Item scores are calculated using a mixture of algorithms and addition but can be summed to give a total minimum score of 0 and a maximum score of 15 with higher scores indicating more problems with sleep. A threshold of >5 has been determined as the threshold for poor sleep (Sancho-Domingo et al., 2021).

7.4.6.6. Short-form jaw functional limitation scale (SF-JFLS)

This is a validated 8-item self-report instrument examining functional limitation in TMD. The instrument's total minimum score is 0 and maximum is 10 which are derived by taking the mean of the eight responses. Higher scores indicate increased functional limitation (Ohrbach et al., 2008).

7.4.6.7. Global impression of change (GIC)

The validated Patient Global Impression of Change scale (Dworkin et al., 2005; Guy, 1976) asks the patient to compare a construct following treatment to prior to treatment and employs a seven-point response scale (scoring in parentheses): very much improved (3) through no change (0) to very much worse (-3). The constructs examined through four items will be: pain intensity; ability to conduct daily

activities; emotional state; overall status. Patients will be asked to select a level of change from the seven-point scale in response to the prompt, "Since the start of the study my [insert construct] is".

7.4.6.8. Liverpool adverse events profile (LAEP)

This is a validated instrument examining the frequency of 25 adverse events whilst taking medications over the last month (Baker, 1993; Baker et al., 1994; Baker, 1994; Baker, 1995; Jasionis et al., 2021; Romoli et al., 2018). It does not ascribe causality and is simply a measure of frequency and quantity of adverse outcomes whilst taking medication(s) (Dang et al., 2021). Its minimum additive score is 25 and its maximum is 100 with higher scores equating to more adverse outcomes experienced at a greater frequency. A threshold value in an Italian population has been established of 36.5 which is predictive of likelihood of terminating use of anti-epileptic medication (Romoli et al., 2018).

7.4.6.9. The Migraine Disability Assessment Test (MIDAS)

This is a validated instrument with five items that examine the impact of headache-related disability on three domains over the last 3 months: school, work or paid (self-) employment; household work or chores; and family, social and leisure activities. It employs an open, but guided, response option for respondents to estimate the number of days (0-90) affected by headache in each of the five items. Scores are calculated by summing the response to each item. Higher scores indicate higher levels of headache-related disability with severe disability (IV) defined >20, moderate (III) defined as 11-20, mild (II) defined as 6-10, and little to no disability (I) defined as 0-5. Its minimum additive score is 0 and its maximum is 450 (Stewart et al 2000). Its minimally important clinical difference has been determined as a change in ≥5 total score (Lipton et al 2017, 2019, 2020).

7.4.6.10. Facial Clinimetric Evaluation (FaCE) scale

This is a validated 15-item instrument examining 6 domains related to facial nerve paralysis: facial movement, facial comfort, oral function, eye comfort, lacrimal control, social function (Kahn et al., 2001). It employs a five-point response scale: strongly agree (1) through don't know (3) to strongly disagree (5). Its total score ranges from 0 (most affected) to 100 (not affected) and is calculated by an algorithm. The scale will only be used if patients opt into its use due to their perception of a facial weakness after an injectable therapy has been applied.

7.4.6.11. Health Utilisation Questionnaire (HUQ)

This is a validated instrument examining two areas (Breckons et al., 2018; Durham et al., 2016b; Durham et al., 2021; Wordsworth and Thompson, 2001): 1) healthcare utilisation in past 3-6 months including visits to clinicians, out-of-pocket expenditure on over-the-counter medication, prescription costs, NHS and private healthcare treatment; 2) productivity in the last 3-6 months including employment status, number of days contracted, number of days absent and present with pain at work, the quantity and quality of work completed (Brouwer et al., 1999) and the work attendance with health problems scale (van Roijen et al., 1996). A reference period of 3 months will be used at Screening (visit 1) and at 12 weeks (visit 3). A reference period of 6 months will be used at 36 weeks (visit 4).

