3.3.1. Primary Endpoint/Outcome

The trial's two co-primary outcomes for effectiveness are:

- Characteristic pain intensity (CPI) assessed by a composite average, worst and current numerical rating scale of pain (0-100 scale (Von Korff et al., 1992)) at 36 weeks of treatment examining last 12 weeks' pain intensity.
- Disorder-specific related quality of life (the Oral Health Impact Profile for TMDs [OHIP-TMD (Yule et al., 2015)]) at 36 weeks of treatment examining the last 4 weeks' quality of life.

The trial's primary economic outcome is:

- incremental cost per quality-adjusted life year gained of the most effective treatment compared to other treatments at 36 weeks calculated using data from the Health Utilisation Questionnaire (HUQ) (administered baseline, 12, & 36 weeks), the time and travel questionnaire (T&TQ administered at census date of 24 weeks), the EQ-5D-5L (administered at baseline, 12, 24 & 36 weeks), and routine sources and study specific estimates for unit costs (Jones and Burns, 2021).

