7.4.4. Further visits (3, 4, and 5)

All participants will have completed the research assessments ahead of the follow-up visit as described in 7.4.6 and if not, further copies will be issued for completion prior to commencing the follow-up visit. Consent will be reconfirmed at each follow-up visit. Follow up and or further treatment will occur at visits 3 (week 12 + - 7 days), 4 (week 24 + - 7 days) and 5 (week 36 + - 7 days).

Follow up visit 3 at week 12 (+/- 7 days), visit 4 at week 24 (+/- 7 days) and follow up visit 5 at week 36 (+/- 7 days), will be conducted in person for all treatment arms. A clinical assessment will take place here, as well as a vital signs assessment. Participants allocated to Botox or Lidocaine will also receive their next cycle of injections at visits 3 and 4. Participants allocated to TAU will have their medication reviewed by the trial investigator and changes made, if required, at visits 3 and 4. Their GP will be written to, if necessary, to ask them to alter their prescription, based on the decision of the trial investigator. Treatment may also be provided by the site pharmacy, depending on local processes.

At the 36 weeks, patients will be returned to the care of their GP as per usual standard of care practice. The GP will discuss and agree with the patient how their care will be conducted after the trial. The research team will contact the patient by telephone 7 days after the 36 week visit to identify any adverse events in that time period. Two attempts will be made to contact the participant.

Case report forms will be completed as required at each trial visit to capture any changes in the medical history, migraine history (if relevant), and if receiving injectable therapy examination status of any facial nerve weakness using the House-Brackmann regional and global scores (Reitzen et al., 2009).

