7.4.10. Schedule of Events

		Day -28 to -1ª (Visit 1)	Day 0 (Visit 2)	Week 12 (Visit 3) +/- 7 days	Week 24 (Visit 4) +/- 7 days	Week 36 (Visit 5) ^c +/- 7 days	Week 37 (+3 days)	Unscheduled Visit - Facial Weakness, medication concern, or other
Activity	Identification potential participants	Face-to-face screening	1 st dose of IMP ^a	Research Assessment IMP review and/ or provision ^b	Research Assessment IMP review and/ or provision ^b	Research Assessment	Phone call	Research Assessment (As/If required)
	Potential participant identification							
Clinical team providing care review clinical notes or databases	х							
Self-referring individual self- screens and makes email contact ¹	х							
Provide PIS +/- invitation letter/email as appropriate	Х							
	Consent & eligibility							
Informed Consent		х		X ^d	X ^d	x ^d		
Dipstick pregnancy Test		х				x ^e		
Confirmation of eligibility		x						
	Routine Data Collection ²							
Sociodemographics		x						
PMH (systems, meds, allergies, daily analgesia use, non-drug therapies)		х						
Medical review (systems, con meds, allergies, daily analgesia use, non-drug therapies)				х	х	х		
Clinical examination inc CN V & VII		X		х	x	х		
Blood pressure, Pulse, Weight, & Height. Height only at day screening		х		х	х	х		
Diagnosis & TMD history		Х						
ID-Migraine +/- Migraine history & MIDAS ²		x		x ^f	x ^f	χ ^f		
	Research assessments (occur prior to		tration or review of					
Pain reporting assessment & feedback		х		Х				

		Day -28 to -1 ^a (Visit 1)	Day 0 (Visit 2)	Week 12 (Visit 3) +/- 7 days	Week 24 (Visit 4) +/- 7 days	Week 36 (Visit 5) c +/- 7 days	Week 37 (+3 days)	Unscheduled Visit - Facial Weakness, medication concern, or other
Activity	Identification potential participants	Face-to-face screening	1 st dose of IMP ^a	Research Assessment IMP review and/ or provision ^b	Research Assessment IMP review and/ or provision ^b	Research Assessment	Phone call	Research Assessment (As/If required)
PHQ-4 & red flag assessment		x		х	Х	х		
GCPS		х						
CPI (within GCPS ³)		x		х	х	Х		
OHIP-TMDs		x		х	х	Х		
EQ-5D-5L		х		х	х	Х		
BPSQI		х		х	х	Х		
SF-JFLS		х		х	х	Х		
GIC				х	х	Х		
LAEP				х	х	Х		
FaCE scale and facial				Optio	onal, as determined by	patient		х
weakness exam								
AE & SAE Reporting		х	х	х	х	Х	x ^g	х
HUQ		х		х		Х		
T&TQ					х			
MRI sub-study assessments: MRI & bone biomarkers ⁴		x (prior to IMP – TAU IMP may be started prior to MRI if it is not possible to delay)				x		

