11.2. Costs

The perspective of the analysis will be the NHS and personal social services (PSS). Additional analyses will widen the perspective to considered costs borne by participants and their families. Intervention costs will be micro-costed and primarily based on the costs of the medications and their administration. Additionally, the costs of managing chronic M-TMD, including the management of adverse events, will also be considered. A bespoke questionnaire, based on the Health Utilisation Questionnaire (HUQ), validated for use in M-TMD, will capture the frequency of participants' primary

and secondary healthcare contacts. The HUQ will be administered at baseline, 12, and 36-weeks post-randomisation. The HUQ will be designed to minimise participant burden while maintaining the accuracy of data as there will potentially be differences in healthcare resource use and hence costs associated with managing M-TMD between the interventions. A broader, societal perspective will also consider direct and indirect costs to participants such as costs to access care and time off work and usual activities due to M-TMD and attending healthcare appointments. This will be measured by the HUQ and a bespoke Time and Travel Questionnaire completed at 24-weeks. Unit costs will be derived using routine data sources and study-specific estimates. Data on the interventions costs and subsequent use of healthcare services will be combined with unit costs to produce a total cost for each trial participant.

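### HUQ recall is set in months for intervals of 12 and 24 weeks, is counted from a different origin than the visits, and carries a wrong visit label at week 36

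*Protocol*

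**What the plan says.** Section 7.4.6.11 fixes the recall of the Health Utilisation Questionnaire (HUQ): "A reference period of 3 months will be used at Screening (visit 1) and at 12 weeks (visit 3", then "A reference period of 6 months will be used at 36 weeks (visit 4". Section 7.4.4 numbers the visits differently: "visit 4 at week 24 (+/- 7 days) and follow up visit 5 at week 36 (+/- 7 days". The Schedule of Events agrees ("Week 24 (Visit 4) +/- 7 days") and marks the HUQ at screening, week 12 and week 36. At week 24 it has only the time and travel questionnaire.

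Section 11.2 states: "The HUQ will be administered at baseline, 12, and 36-weeks post-randomisation". It then has intervention costs and service use "combined with unit costs to produce a total cost for each trial participant". Section 7.4.3, however, counts visit dates from Day 0, the start of treatment, and section 7.4.2 allows up to 28 days between screening, where randomisation takes place, and that start.

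These costs feed the primary economic outcome in section 3.3.1, the "incremental cost per quality-adjusted life year gained of the most effective treatment compared to other treatments at 36 weeks". Section 11.4 gives the within-trial horizon as 36 weeks.

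**The concern.** Two post-baseline forms have to account for all resource use over the within-trial horizon, so their recall windows should meet without overlap or gap. Three features put that in doubt.

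- The week-36 form is tied to the visit number that belongs to week 24.
- Recall is in months and visits are in weeks, and 3 and 6 calendar months are longer than 12 and 24 weeks.
- The economics section starts its clock at randomisation, but the visits start theirs at Day 0.

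At stake is the cost side of the primary economic outcome. Use reported on both forms would be summed twice, and use that falls in neither window would be lost. Section 11.2 describes the HUQ as capturing how often contacts occur and mentions no contact dates. If only counts are held, overlapping contacts cannot be identified and removed afterwards.

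**Working it through.** **Visit label.** Section 7.4.6.11 puts week 36 at visit 4. Section 7.4.4 and the Schedule of Events put week 24 at visit 4 and week 36 at visit 5. Sections 3.3.1 and 11.2 give the HUQ time points as baseline, 12 and 36 weeks. The week is consistent throughout; only the visit number is wrong.

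**Recall windows at nominal visits.** Each window runs from (visit week − recall) to the visit week. The target is weeks 0–12 plus weeks 12–36, which is 36 weeks. The protocol states no total recall coverage of its own to reproduce. One calendar month is taken as 365.25/12 days.

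| Reading of the recall | 3 months | 6 months | Sum | Excess over 36 | Week-12 form starts | Week-36 form starts | Overlap before week 12 |
|---|---|---|---|---|---|---|---|
| Calendar months | 13.04 wk | 26.09 wk | 39.13 wk | 3.13 wk | week −1.04 | week 9.91 | 2.09 wk |
| Rounded to whole weeks | 13 | 26 | 39 | 3 | week −1 | week 10 | 2 |
| 3 months = 12 weeks | 12 | 24 | 36 | 0 | week 0 | week 12 | 0 |

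The 3-week excess is therefore about 2 weeks asked about twice plus about 1 week before Day 0.

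**Size at nominal visits, assuming even use over time.**

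- Whole excess: 3/36 = 8.3% (3.13/36 = 8.7% unrounded).
- With 90 days per 3 months: (90 + 180 − 252)/252 = 18/252 = 7.1%.
- Overlap alone: 2/36 = 5.6% (2.09/36 = 5.8% unrounded).
- With 3 months = 12 weeks: 0.

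**Effect of the ±7-day visit windows.** Overlap is the 6-month recall minus the interval from visit 3 to visit 5.

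- Longest interval, 37 − 11 = 26 weeks: 26.09 − 26 = 0.1 weeks of overlap.
- Shortest interval, 35 − 13 = 22 weeks: 26.09 − 22 = 4.1 weeks of overlap.
- With a 24-week recall the same extremes give a 2-week gap and a 2-week overlap, so restating the recall in weeks would not make the windows meet.

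**Time origin.** Let L be the lag from randomisation to Day 0, from 0 to 4 weeks. At a nominal week-12 visit the first post-baseline recall starts 1.04 weeks before Day 0 on calendar months, or at Day 0 on a 12-week recall.

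- Uncovered time at L = 4: 4 − 1.04 = 2.96 weeks on calendar months; 4 − 0 = 4 weeks on a 12-week recall.
- Randomisation to the week-36 visit is 36 + 4 = 40 weeks. Summed recall against that is 39.13/40 − 1 = −2.2% on calendar months and 36/40 − 1 = −10% on a 12-week recall.

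On the randomisation clock, the net error can thus run in either direction.

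**The case against.** The strongest reply is that the protocol itself treats 3 months as 12 weeks. Section 7.1.5 describes 3-monthly injections at weeks 0, 12 and 24. The recall for characteristic pain intensity is 12 weeks in section 3.3.1 and three months in section 7.4.6.2. On that usage the HUQ windows meet exactly at nominal visits. This stands as a limit on the claim: a reader might infer that the recalls certainly cover 39 weeks, and the documents do not establish that. But respondents answer the wording put to them, and section 7.4.6.9 pairs a 3-month recall with a range of 0–90 days, which fits calendar months better than 84 days.

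Other strong readings also fail.

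- A reader might infer that the second post-baseline HUQ is given at week 24, repeating weeks 0–12 and missing weeks 24–36. Only the one label supports this; every other statement says week 36.
- A reader might infer that the week-12 visit is itself counted twice. Section 7.4.4 has the forms completed before the visit begins, so that visit can fall only in the week-36 recall.
- A reader might carry the 8% over to the incremental cost. About one of the three excess weeks precedes treatment, when no treatment-related difference between arms is expected. All arms use the same form, and separately micro-costed intervention costs are untouched.

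Finally, section 11.1 leaves the detail to a Health Economics Analysis Plan, which is not shown and may truncate or scale the recall. That is a fair reason not to say the costs will go uncorrected. It does not change recall wording that is fixed when the data are collected.

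**Conclusion.** The visit label is wrong by the protocol's own numbering and is a slip. The recall mismatch is real but conditional. With calendar-month recall, even use and visits on target, HUQ-based costs measured from Day 0 are overstated by about 8%, of which about 6% comes from the overlap before week 12. With 3 months read as 12 weeks the figure is 0, so the range is 0 to about 8%. For a HUQ-based cost difference between arms, the overlap share is the relevant upper figure under the same assumptions.

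The conflict of time origins does not depend on how months are read. Where treatment starts late, up to about 3 weeks after randomisation (4 with a 12-week recall) fall in no post-baseline window, and this can offset or outweigh the overlap. The documents therefore support a recall design that leaves avoidable overlap and gaps in a primary economic outcome. They do not support a definite overstatement of cost.

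**What to change.** - In section 7.4.6.11, change the visit label for week 36 from 4 to 5.
- Replace the fixed post-baseline recalls with dated anchors filled in by the e-form. The week-12 form would ask about the time *since your screening questionnaire/randomisation on [date]*. The week-36 form would ask about the time *since your week-12 questionnaire on [date]*. This removes both the overlap and the gap whatever the visit timing.
- Use the same time origin in section 11.2, and have the Health Economics Analysis Plan say how costs and QALYs are aligned. With recall running from randomisation, the period to a nominal week-36 visit is 36 to 40 weeks.
- For forms already completed, rescale to the intended interval only as a sensitivity analysis. Factors of 12/13 and 24/26 presume calendar-month reading; if respondents meant 12 and 24 weeks, they would understate HUQ costs by 1 − 12/13 = 7.7%. Anchoring the week-12 form to treatment start would likewise drop use between randomisation and Day 0.

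The cost is a short protocol edit, e-form wording and matching text in the analysis plan. The small downside is a change in recall wording part-way through the trial, so the form version should be recorded.

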7.4.6.12. Time and travel questionnaire (T&T)

This validated instrument collects data on all healthcare visits (Breckons et al., 2018; Durham et al., 2016b; Durham et al., 2021; Wordsworth and Thompson, 2001): the distance, duration, and usual mode of transport, in addition to any childcare or accompanying person required and any activities foregone for the visit.

7.4.7. Pain reporting assessment & feedback

All participants will undergo an assessment of their pain reporting and be given feedback on this at visit 1 (screening) and visit 3 (week 12), based on methods reported by Treister *et al* (2018) which have been shown to diminish the placebo response in pharmacological trials (Treister et al., 2018). Pain threshold (lowest stimulus intensity that is perceived as painful, corresponding to 1 on a 0–10 numerical rating scale [NRS]) and pain tolerance (maximal tolerable stimulus intensity, corresponding to 10 on a 0–10 NRS) will be measured at the thumbnail of the dominant hand using an algometer (FPN 100; Wagner Instruments, USA). The measurement can still be taken if the participant has false / acrylic nails, and the wearing of false / acrylic nails will be recorded in the database. Three stimulus levels (threshold, 75% of tolerance, and a stimulus equidistant to the prior two) will each be applied for 3 seconds, each on four occasions in a random order with a 20-second interstimulus period. Participants will rate each stimulus immediately following application on a 0–10 NRS. Feedback will be given to participants after the first six stimuli, and again after all 12 stimuli, on how accurately their reported pain scores reflect the applied stimulus intensities by plotting responses on a scatter chart to identify outliers and by calculating R².

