3.3.2. Secondary Endpoints/Outcomes

The secondary outcomes are:

- CPI at 12 and 24 weeks
- OHIP-TMD at 12 and 24 weeks
- 30% and 50% reduction from baseline in CPI
- 30% and 50% improvement from baseline in OHIP-TMD
- Health Utilisation Questionnaire (HUQ) alongside time and travel questionnaire (T&TQ) (Durham et al., 2016b)
- EQ-5D-5L (Herdman et al., 2011)
- Jaw function limitation questionnaire short-form (Ohrbach et al., 2008)
- PHQ-4, psychosocial distress (Kroenke et al., 2009)
- Brief Pittsburgh Sleep Quality Index (Sancho-Domingo et al., 2021)
- Over-the-counter (OTC) analgesia use (Dworkin et al., 2008)
- Structural changes and apparent diffusion coefficient (representing bone density) in the TMJ on MRI (Muraoka et al., 2021) and serum biomarkers of bone turnover CTX and P1NP (Szulc et al., 2017)
- Global impression of change in pain intensity, daily activities, emotional status, and overall status (Dworkin et al., 2008)
- Liverpool adverse effects profile (Baker, 1995; Besi et al., 2015)

- Longitudinal sequential qualitative data collection from purposive sub-sample of participants using semi-structured interviews.
- Pain reporting accuracy from the pain reporting assessment and feedback study procedure.
 This will be reported as pain threshold, pain tolerance, and R² values from applied pressure stimuli and participant's reported pain intensity.

A longer-term economic model will also be explored extrapolating costs and outcomes over a lifetime horizon.

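### The first pain-reporting feedback follows six of 12 randomly ordered stimuli with no stated balance of levels, so the R² fed back partly reflects the draw of the order; two balanced blocks of six would remove this

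*Protocol*

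**What the plan says.** Protocol section 7.4.7 describes the procedure. "All participants will undergo an assessment of their pain reporting", at screening (visit 1) and at week 12 (visit 3). The stimuli are "Three stimulus levels (threshold, 75% of tolerance, and a stimulus equidistant to the prior two"), and they are applied "each on four occasions in a random order with a 20-second interstimulus period". Then: "Feedback will be given to participants after the first six stimuli, and again after all 12 stimuli". Accuracy is shown to the participant "by plotting responses on a scatter chart to identify outliers and by calculating R²". The method is taken from a cited study and is described as one of those "which have been shown to diminish the placebo response in pharmacological trials", so the feedback is meant to change how participants report.

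R² is also an analysis variable. Section 3.3.2 lists pain reporting accuracy among the secondary outcomes: "This will be reported as pain threshold, pain tolerance, and R² values from applied pressure stimuli" and the reported pain intensity. The trial summary lists it as exploratory and plans to examine whether reporting accuracy influences trial outcome. Neither place says which stimuli, or which visit, enter the R² that is analysed.

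**The concern.** R² depends on the spread of the stimuli as well as on the reporter. If the first six stimuli over-represent one level, or omit an end level, the same reporter can get a different score. That score is fed back as a measure of accuracy, so part of the coaching signal is chance in the order.

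The second issue is what a full-session R² describes. The feedback after stimulus six is intended to alter reporting. An R² over all 12 would combine six reports made before it with six made after it. If that R² is the variable related to trial outcome, it is a blend of two states whenever the feedback works.

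The order matters more than a choice of analysis would. Which R² to analyse can be settled later from stored responses, but a session already delivered with a level missing from its first half cannot be rebalanced. Reports free of any earlier coaching exist only in stimuli 1–6 at visit 1, because visit 3 follows the visit 1 feedback.

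**Working it through.** **Inputs.** Protocol section 7.4.7: three levels, four repeats, feedback after stimuli 6 and 12, two sessions. Protocol section 7.1: 663 participants. Assumption: each order is a simple random permutation of the 12 stimuli, since no restriction is stated.

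**The plan's own figure.** 3 × 4 = 12 stimuli, which agrees with the protocol.

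**Exact composition of the first six.** There are C(12,6) = 924 equally likely ways to choose which six stimuli come first.

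| Split across the three levels | Count | Share |
|---|---|---|
| 2/2/2 | C(4,2)³ = 216 | 23.4% |
| 1/2/3 | 576 | 62.3% |
| 1/1/4 | 48 | 5.2% |
| 0/3/3 | 48 | 5.2% |
| 0/2/4 | 36 | 3.9% |

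- Unbalanced: (924 − 216)/924 = 76.6%; 663 × 0.766 ≈ 508 per visit.
- A level absent: 3 × C(8,6)/924 = 84/924 = 9.1%; 663 × 0.091 ≈ 60 per visit.
- An end level absent (threshold or 75% of tolerance): 2 × 28/924 = 56/924 = 6.1%; 663 × 0.0606 ≈ 40 per visit.
- Over two sessions: at least one unbalanced first half, 1 − 0.234² = 94.5%; at least one with a level absent, 1 − (1 − 0.0909)² = 17.4%.

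The head counts suppose that all 663 are tested at the visit. Fewer will be at week 12.

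**Effect on the R² fed back (simulation; parameters assumed, none in the protocol).** Ratings run linearly from 1 at threshold to 10 at tolerance and are rounded to 0–10. Threshold is 30% of tolerance, with 20,000 sessions.

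- Error SD 1 NRS point: mean first-half R² is about 0.89 if balanced, 0.87 for a 1/2/3 split, 0.73 with an end level absent and 0.92 with the middle level absent. Over all random orders the mean is 0.87 and the SD across sessions 0.107, against an SD of 0.082 when balanced.
- Error SD 2: mean 0.64 over all random orders against 0.67 if balanced, with SDs of 0.235 and 0.212.
- A simpler model (2 NRS points per level, no rounding, error SD 1.5 to 2.0): 0.51 to 0.64 if balanced, 0.42 to 0.53 with a level absent.

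**Effect of pooling before and after feedback (assumed size of the feedback effect).**

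| Model; error SD before → after | Stimuli 1–6 | Stimuli 7–12 | All 12 |
|---|---|---|---|
| 2 points per level; 1.5 → 1.0 | 0.61 | 0.77 | 0.66 |
| 2 points per level; 2.0 → 1.0 | 0.49 | 0.77 | 0.57 |
| Threshold 30% of tolerance; 2 → 1 | 0.64 | 0.87 | 0.73 |

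**Is a six-point R² the better measure of untrained accuracy?** With threshold at 20–50% of tolerance and varied error and feedback effects, the correlation between R² and the reporter's true error SD before feedback was about −0.54 to −0.58 for block 1 alone and −0.65 to −0.72 for all 12. In these runs the longer series gained more in precision than it lost by pooling.

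**The case against.** The case on the other side has weight in five places.

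- The absence of blocking is inferred from silence. A random order may still be restricted in a working instruction or in the cited method, which the protocol does not reproduce. This stands, so every percentage is conditional on simple randomisation.
- The imbalance is mostly mild. The usual split, 1/2/3, contains all three levels and costs little: across all orders, blocking raises mean R² by only about 0.02 to 0.03, and most of the spread remains because R² rests on six points. This stands. A reader might infer that most participants are coached on an incomplete set; only 9.1% are, and losing the middle level raises R² rather than lowering it.
- The second feedback always rests on four stimuli per level, so each completed session ends on a balanced set. This stands, but it does not correct the first feedback, which precedes half of the ratings.
- A reader might infer that the protocol fixes the outcome R² over all 12 stimuli. It does not. The plural in section 3.3.2 allows separate values, and the choice can be left to the SAP. Pooling is therefore a conditional concern.
- A reader might also infer that accuracy has to mean untrained accuracy, so that visit 1 stimuli 1–6 should replace the full series. The stated objective does not ask for that. Later CPI reports all follow the visit 1 feedback, and the six-point value tracked untrained accuracy less well in simulation.

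What survives is that order and feedback timing are site procedures, and no later analysis can rebalance a session already given.

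**Conclusion.** The point holds in a limited form. As written, the protocol does not ensure that the first feedback rests on a balanced or complete set of levels. Under a simple random order, 76.6% of first halves are unbalanced, 9.1% lack a level and 6.1% lack an end level. Those shares are exact given that assumption. The last group, about 40 of 663 per visit, is where the R² shown to the participant is materially lowered: about 0.73 against 0.89 in one assumed scenario. An R² over all 12, if chosen as the outcome, would also blend reports from before and after the mid-session feedback. All R² values here depend on assumed thresholds, errors and feedback effects.

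The importance is low. It would be wrong to read this as a threat to the primary comparison: the procedure is the same in every arm, visit 1 testing precedes randomisation, and R² enters neither the co-primary models (section 10.2.1) nor the sample size (section 10.3). What is affected is the coaching itself, the pain-reporting-accuracy outcome and its planned exploratory use.

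**What to change.** In section 7.4.7, state that the 12 stimuli are given in two blocks of six, each block holding every level twice in random order. This raises the chance of a balanced first half from 23.4% to 100% and lowers the chance of an absent level from 9.1% to zero. If a working instruction already restricts the order, say so in the protocol.

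State which stimuli and visit define the R² outcome. Keep the 12-stimulus R², and also report the block 1 and block 2 values separately by visit as a supplementary view of accuracy before and after feedback. Note that six-point values are noisier and do not simply replace the 12-stimulus value, and that at visit 3 both blocks follow earlier coaching. For participants already tested, the two halves can be computed if individual responses were stored, although their balance cannot be restored.

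The cost is a new order list for sites and a few sentences of text. Session length and the number of stimuli do not change.
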